10 STATISTICAL / ANALYTICAL ISSUES

10.1 Handling of Dropouts or Missing Data

All data will be used to their maximum possible extent, but without any imputations for missing data. All time-to-event analyses will include censoring and the rules for deriving the censored values are described in more detail under each of the time-to-event endpoint descriptions.

10.2 Pooling of Centers in Multi-Center Studies

All centers will be pooled for analysis.

10.3 Multiple Comparison / Multiplicity

No adjustments for multiple comparisons will be made.

10.4 Examination of Subgroups

Analyses of efficacy, safety, and exploratory endpoints may be analyzed by baseline demographics and clinical characteristics listed in [Sections 6.1](#) and [6.2](#) or for other subgroups of interest as appropriate.

10.5 Interim Analyses and Data Monitoring

A group sequential interim monitoring plan will be implemented in order to help guide the data monitoring committee (DMC) in monitoring the study. The null hypothesis is $p=0.10$ based on historical data in similar patient populations. The study has greater than 90% power to reject the null hypothesis at a 5% significance level if the true response rate for rucaparib is 20%.

Interim analyses will be performed when approximately 60 patients and 120 patients have complete data, defined as a documented response (PR or CR), disease progression, or at least 4 months of disease assessment data available.

If the response rate does not meet continuance criteria for the ITT population, the DMC will further evaluate the benefit: risk for study treatment, both overall and separately for patients in different HRD subgroups, and make a recommendation whether further enrollment into 1 or all groups should be discontinued.

Additional details regarding this group sequential interim monitoring plan are provided in [Appendix 2](#).

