11.6 Data Monitoring Committee

A DMC will be established to review safety data in compliance with a prospective charter. The DMC will comprise coordinating investigators and sponsor representatives. The DMC responsibilities, authorities, and procedures for this study will be documented in the DMC Charter, which will be endorsed by the DMC members and signed by the DMC chair prior to the first data review meeting. The DMC will also ensure the study is beneficial to patients (see [Section 9.10](#)).

The DMC will meet after the first 20 patients received rucaparib for at least 28 days or discontinued study treatment, and then approximately every 6 months after sufficient data have been collected. Safety and efficacy will be assessed by the DMC at the interim analyses at 60 and 120 patients. The DMC chairperson or sponsor may convene an unscheduled DMC meeting if there are newly identified significant safety concerns. Following data review, the DMC will recommend continuation, revision, or termination of the study and/or continuing or halting enrollment into a particular subgroup. Details regarding the DMC will be in the committee charter.

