3.1 Analysis Populations

The following analysis populations are defined for the study:

Safety Population – The safety population will include all patients who received at least 1 dose of rucaparib.

Intent-to-treat Population (ITT) – The ITT population will include all patients who received at least 1 dose of rucaparib.

HRD-positive Population – The HRD-positive population will include all patients who received at least 1 dose of rucaparib and are classified as HRD-positive by the prospectively-defined HRD signature (See [Section 3.2](#)).

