Appendix 2 Group Sequential Interim Monitoring Plan

Introduction

This plan describes an adaptive study design for the evaluation of rucaparib in patients with locally advanced or metastatic urothelial carcinoma. The adaptive design utilizes interim analyses that allow for early stopping for futility after DMC review of futility analysis of the ITT population, the efficacy for HRD subgroups and all safety analyses.

The trial will enroll 60-200 subjects in a single experimental arm.

Objective response rate by RECIST v1.1 as assessed by the investigator will be summarized for the ITT and HRD-positive populations as well as for the exploratory HRD groups.

Primary Analysis

Let p be the true response rate. The primary analysis compares p to a performance goal of 0.10, and is thus a hypothesis test of

$$H_0 : p \leq 0.10 \quad H_1 : p > 0.10$$

Starting with a noninformative Beta(0.1,0.9) prior on p , the posterior distribution is

$$p|\text{data} \sim \text{Beta}(0.1+Y, 0.9+N-Y)$$

where Y is the observed number of responses and N is the number of complete subjects in the trial. The trial is a success if

$$\Pr(p > 0.10 | \text{data}) > 0.95$$

This threshold maintains type I error at 5%. We consider an alternative threshold (0.935) that increases type I error slightly but obtains greater power for comparison.

Design

The trial sequentially enrolls patients and interim analyses are conducted. At the time of each interim analysis, there will be N patients with a 4-month endpoint and M patients that are incomplete. Let Y be the number of responders among the complete patients.

The model computes p_{\max} , the predictive probability of trial success if the trial is followed to the maximum (targeted) sample size and all patients are followed to completion. Let W_{\max} be the number of eventual responders among the unknown patients (incomplete and currently unenrolled). The distribution of W_{\max} is a BetaBinomial(MAXN-N, 0.1+Y, 0.9+N-Y). The predictive probability p_{\max} is the probability W_{\max} results in trial success when N=200 subjects are complete.

The model indicates trial futility at any interim analysis if $p_{\max} < \text{threshold}$, indicating that there is limited probability that the trial will reach success even at the maximum sample size.

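### If one HRD group is closed after a failed ITT interim, the ITT test and ITT ORR still pool all dosed patients, so 5% type I error is not assured when the HRD groups respond differently

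*SAP*

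**What the plan says.** A missed ITT continuation limit does not by itself stop the trial. Under SAP 10.5 and Protocol 9.10 the DMC then weighs benefit and risk overall and by HRD subgroup, and may "make a recommendation whether further enrollment into 1 or all groups should be discontinued". Protocol 11.6 repeats this power as "continuing or halting enrollment into a particular subgroup".

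The ITT definition makes no allowance for such a closure: "The ITT population will include all patients who received at least 1 dose of rucaparib" (SAP 3.1; Protocol 9.2 agrees). SAP Appendix 2 (Protocol Appendix 4) sets the test: "The primary analysis compares p to a performance goal of 0.10, and is thus a hypothesis test of" p ≤ 0.10 against p > 0.10. Success is a posterior probability above 0.95, computed from all complete subjects. On error control it says: "This threshold maintains type I error at 5"%.

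The interim limits are 5/60 and 13/120, with a maximum of 200. The simulations use one response rate for everyone, and each trial stops at 60, stops at 120 or runs to the maximum. Missing a limit does not end the ITT test: in Example Trial 2, 3/60 fails the first look and the posterior is still evaluated on 12/100.

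**The concern.** Before a closure, ITT patients are an unselected HRD mix, planned at 60% positive. If HRD-negative enrolment closes and HRD-positive enrolment continues, every later ITT patient is HRD-positive. The pooled rate then no longer describes the unselected population, yet it is still reported as ITT and tested against the same 10% goal. If HRD-positive patients respond more often, the change of mix helps the ITT test succeed after the ITT data have already missed a limit.

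At stake are the meaning of one of the two primary results and the 5% error statement attached to it. Under the null, the plan's own table has about 60% of trials missing a limit (0.270 + 0.331 = 0.601), so the DMC would reach this decision point often.

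**Working it through.** **Inputs from the documents.** Null rate 0.10; Beta(0.1, 0.9) prior; success threshold 0.95; maximum N = 200; limits 5/60 and 13/120; 60% HRD-positive (SAP 2.3). Overrun is 40 patients at the first look and 27 to 31 at the second in the worked examples (29 used). The stated accrual of 1.5 per week over about 17 weeks gives about 26.

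**Inputs assumed.** The HRD-positive rate p+ and HRD-negative rate p−, always with 0.6·p+ + 0.4·p− = 0.10, so the all-comer rate is exactly null. Example: 0.6 × 0.15 + 0.4 × 0.025 = 0.09 + 0.01 = 0.10.

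**1. Reproduce the plan.** The success limit is the smallest Y with Pr{Beta(0.1 + Y, 200.9 − Y) > 0.10} > 0.95. Y = 27 gives 0.9355 and Y = 28 gives 0.9585, so 28/200 is needed.
- Fixed N: Pr{Bin(200, 0.10) ≥ 28} = 0.0434 (stated 0.043); at 0.20 it is 0.989 (stated 0.989).
- With futility stops, exact: 0.0415 (stated 0.039; 10,000 simulations, SE about 0.002).
- Stops under the null: 0.271 and 0.332 (stated 0.270 and 0.331).

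**2. Add the branch.** Let o1 and o2 be the unselected overrun at the two looks. Patients after the overrun are all HRD-positive, total N is refilled to 200, and success stays at 28/200. False ITT success is A + B + C:
- A: both looks passed, then at least 28/200 = 0.0415.
- B: Y60 < 5, then Y60 + Bin(o1, 0.10) + Bin(140 − o1, p+) ≥ 28, with or without requiring at least 13 at patient 120.
- C: first look passed, Y120 < 13, then Y120 + Bin(o2, 0.10) + Bin(80 − o2, p+) ≥ 28.

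At 15%/2.5% with overrun 40 and 29 and the second look kept, this is 0.0415 + 0.0173 + 0.0096 = 0.0684. With the second look dropped it is 0.0415 + 0.0283 + 0.0096 = 0.0794.

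**3. Results, always closing HRD-negative after a missed limit** (each pair: second look kept, then dropped)

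| p+ / p− | Overrun 40 and 29 | No overrun |
|---|---|---|
| 10% / 10% | 0.043, 0.043 | 0.043, 0.043 |
| 12% / 7% | 0.048, 0.049 | 0.053, 0.055 |
| 13% / 5.5% | 0.053, 0.056 | 0.066, 0.070 |
| 15% / 2.5% | 0.068, 0.079 | 0.117, 0.127 |

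With 26 overrun patients and the second look dropped, the last three rows become 0.051, 0.059 and 0.090; keeping the look brings the 0.090 down to 0.079. In the 40/29 column the error passes 5% at p+ of about 0.121 to 0.125.

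**4. A more selective DMC.** Suppose HRD-negative closes only when the observed HRD-positive ORR is at least 10% and above the HRD-negative ORR, and the trial otherwise stops. With 26 to 40 overrun, simulation gives about 0.044 at 12%/7%, from about 0.047 at 13%/5.5%, and about 0.06 to 0.07 at 15%/2.5%.

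**5. Effect on the mix.** Closure at the first look with 26 overrun leaves 86 unselected and 114 HRD-positive patients. The HRD-positive share is (0.6 × 86 + 114)/200 = 82.8%. At 15%/2.5% the true rate of that mix is (86 × 0.10 + 114 × 0.15)/200 = 12.85%, against 10% in all-comers.

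**6. Under the fix.** Testing only patients enrolled before closure gives limits of 14/86 and 22/146 (26 overrun), or 16/100 and 22/149 (40 and 29). Total error is 0.0415 to 0.0416. Ending the ITT claim at selective closure gives 0.0415.

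**The case against.** A reader might infer that the 5% error rate is simply lost. The documents do not support that. At the null the plan simulates, 10% in every patient, closing a group changes nothing about the response rate. Ignoring the futility stop at most restores the fixed-N error of 0.0434. Inflation needs unequal HRD rates, and the documents give no subgroup rates.

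A reader might also take 0.09 as the error at 15%/2.5%. That value needs HRD-negative to close after every missed limit, only 26 overrun patients, refill to 200, and the 13/120 look dropped after closure at 60. The plan specifies none of these for this branch. Appendix 2 applies the futility rule at any interim, and the DMC may instead stop all groups. If enrolment ended at about 120 HRD-positive patients, the number the sample size targets, the error would be roughly 0.05.

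Two further points stand in part. First, patients enter whatever their HRD status, and tissue may arrive as late as Cycle 2 Day 1, so closing one group would need an enrolment change, presumably by amendment, which could also settle the ITT rule. That shows the branch is underspecified; the DMC's stated power remains. Second, if p is read as the rate in whoever was dosed, an enriched mix truly exceeds 10% and success is not false. That result would not be an all-comer claim, so the target population has to be stated under either reading.

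**Conclusion.** The gap is real and conditional. The plan permits selective closure, keeps the pooled ITT definition and test, and quotes a 5% error from simulations that omit this path. With all-comer ORR at 10%, 60% HRD-positive, 26 to 40 overrun patients and refill to 200, false ITT success is:
- at most about 0.044 with equal rates;
- about 0.044 to 0.051 at 12%/7%;
- about 0.047 to 0.059 at 13%/5.5%;
- about 0.06 to 0.09 at 15%/2.5%.

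Within each range the value depends on the closure rule, the overrun and whether the 13/120 look is kept. At 15%/2.5% the extreme is about 0.127, with no overrun and no second look. The conclusion is that 5% is not assured if the HRD groups differ. That condition matters because HRD-dependent activity is the trial's premise, and an apparent difference is the likeliest reason to close only one group.

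**What to change.** In SAP 10.5/Appendix 2 and Protocol 9.10/Appendix 4, state that if enrolment of one HRD group is closed, the ITT success test and the all-comer ORR use only patients enrolled before the closure took effect. Later patients count towards the ORR of the HRD group that stays open and towards safety. A simpler alternative is to state that selective closure ends the ITT success claim.

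Cross-reference the rule in the ITT definitions (SAP 3.1, Protocol 9.2), which would otherwise contradict it. State that the 5% error and the operating-characteristic tables apply under it.

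The cost is a few sentences. After a closure the ITT test rests on fewer patients (about 86 to 100, or about 146 to 149), but by then ITT success at full enrolment already had under 5% predictive probability.

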11 SAFETY ANALYSIS

The safety analyses will be performed using the safety population.

11.1 Adverse Events

Adverse events will be classified using the MedDRA classification system. The severity of the toxicities will be graded according to the National Cancer Institute (NCI) Common Terminology Criteria for Adverse Events (CTCAE) whenever possible. Treatment-emergent adverse events (TEAEs) are defined as AEs with onset date on or after the date of first dose of study medication until the date of the last study medication dose plus 28 days. Adverse events will be considered treatment-emergent if all or part of the date of onset of the AE is missing and it cannot be determined if the AE meets the definition for treatment-emergent.

The number and percentage of patients who experienced TEAEs for each system organ class and preferred term will be presented. Multiple instances of the TEAE in each system organ class and multiple occurrences of the same preferred term are counted only once per patient. The number and percentage of patients with at least one TEAE will also be summarized.

The incidence of TEAEs will also be summarized by relationship to study drug according to the following categories: “treatment-related,” or “not treatment-related”. If a patient

experiences multiple occurrences of the same AE with different relationship categories, the patient will be counted once, as a relationship category of treatment-related.

If a patient experiences multiple occurrences of the same AE with different toxicity grades, the patient will be counted once for the maximum (most severe) toxicity grade. AEs with a missing toxicity grade will be presented in the summary table with a toxicity grade of "Missing." For each toxicity grade, the number and percentage of patients with at least one TEAE of the given grade will be summarized.

The time to the first TEAE and first treatment-related TEAE that results in a dose reduction, delay, interruption, or discontinuation of study drug is defined as 1+ the number of days from the first dose of study drug to the start of the first TEAE.

Separate tables will be presented including but not limited to:

- All TEAEs;
- TEAEs by CTCAE grade;
- Grade 3 or greater TEAEs;
- Treatment-related TEAEs, overall and by categories: CTCAE grade, grade 3 or greater, resulting in dose reduction, resulting in dose interruption, resulting in dose discontinuation, outcome of death;
- Serious TEAEs, overall and by categories: age, sex, and treatment-relatedness;
- TEAEs with an outcome of death;
- TEAEs leading to discontinuation of study medication;
- TEAEs resulting in interruption of study medication; and
- TEAEs resulting in reduction, delay, or interruption of study medication.
- Time to the first TEAE that results in a reduction, delay, interruption, or discontinuation of study drug.
- Time to the first treatment-related TEAE that results in a reduction, delay, interruption, or discontinuation of study drug.

Non-TEAEs (pre-treatment and post-treatment) will be presented in the by-patient data listings for the safety population.

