Rationale 
Bladder cancer is the ninth most common cancer worldwide and amongst the 6 most common cancers in the United States (US) and Europe.^{1,2} In the US, it is estimated that there will be over 79,000 new cases of bladder cancer and over 16,000 deaths from bladder cancer in 2017.¹ Muscle invasive bladder cancer (MIBC) is a platinum-sensitive disease with cisplatin-containing chemotherapy being the preferred first-line treatment in the adjuvant setting.³ Although the initial response rate for cisplatin-containing chemotherapy ranges from 49% to 72%, most patients will have disease relapse within 9 months.^{4,5} For patients ineligible to receive cisplatin, treatment with carboplatin-containing chemotherapy or an immune checkpoint inhibitor is typically administered in the first-line setting; however, the response rate and time to progression are less than cisplatin-containing chemotherapy.³ After disease relapse, the choice of treatment in the second-line setting includes immune checkpoint inhibitors, single-agent docetaxel, single-agent paclitaxel, and single-agent vinflunine. A majority of patients will have progression of their disease within 2 to 3 months of starting treatment for relapsed disease.⁶ Options are limited after treatment with platinum-containing chemotherapy and/or an immune checkpoint inhibitor, therefore additional therapies are needed.
 
Inhibition of deoxyribonucleic acid (DNA) damage repair in cancer cells represents an attractive opportunity for the development of new therapies. In normal cells, single-strand breaks (SSBs) in DNA are repaired through base excision repair (BER) via poly(adenosine diphosphate [ADP]-ribose) polymerase (PARP) enzymes. SSBs that are not repaired result in stalled replication forks and the development of double-strand breaks (DSBs), which are in turn primarily repaired by homologous recombination repair (HRR) of DNA, a complex process involving multiple proteins. Given the overlap in various DNA repair pathways, inhibition of a single pathway is unlikely to have a significant effect on cancer cell death. However, inhibition of multiple DNA repair pathways may lead to cell death, a concept known as synthetic lethality. For example, normal cells treated with a PARP inhibitor still have other intact DNA repair pathways that are able to survive, whereas cancer cells with pre-existing homologous recombination deficiency (HRD) that are treated with a PARP

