3 GENERAL ANALYSIS CONVENTIONS

Quantitative variables will typically be summarized using frequencies and percentages for appropriate categorizations and may also be summarized using descriptive statistics. For variables summarized with descriptive statistics, the following will be presented: N, mean, standard deviation (StD), median, minimum, and maximum. Categorical variables will be presented using frequencies and percentages.

The Kaplan-Meier methodology will be used to summarize time-to-event variables.^{1,2} Estimates of the proportion surviving across time will be plotted, and if estimable, the 50th (median) percentile with the corresponding 95% confidence interval (CI) will be presented. The number of patients with events and the number of censored patients over time will also be displayed.

Baseline is defined as the last measurement on or prior to the first dose of rucaparib administration, unless otherwise specified.

All statistical analyses will be conducted with the SAS[®] System, Version 9.3 or higher.

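### Kaplan-Meier with no stated censoring rule would overstate the risk of a first dose-modifying TEAE if patients who stop rucaparib are censored at that point

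*SAP*

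**What the plan says.** SAP section 11.1 lists among its safety tables "Time to the first TEAE that results in a reduction, delay, interruption, or discontinuation of study drug", and a second version limited to treatment-related TEAEs. The variable "is defined as 1+ the number of days from the first dose of study drug to the start of the first TEAE". Section 11.1 names no summary method, gives no censoring rule, and is silent on patients who leave treatment without the event.

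Two general rules fill part of the gap:

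- SAP section 3: "The Kaplan-Meier methodology will be used to summarize time-to-event variables". No exception is made. The summary consists of a curve ("Estimates of the proportion surviving across time will be plotted") and, where estimable, a median with its 95% CI.
- SAP section 10.1: "All time-to-event analyses will include censoring and the rules for deriving the censored values are described in more detail", the place for that detail being the individual endpoint descriptions. Sections 9.2.1 to 9.2.3 give such rules for DOR, PFS and OS. Section 11.1 gives none.

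The same section closes the TEAE window 28 days after the last dose. It also reports TEAEs as numbers and percentages of patients, with separate tables for discontinuation, for interruption, and for reduction, delay or interruption.

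**The concern.** Once rucaparib has been stopped for good, there is no dose left to reduce, delay, interrupt or discontinue. Stopping for another reason, and death, therefore rule the event out. They do not merely hide it from view. Kaplan-Meier with these patients censored assumes that they would have gone on to dose-modifying toxicity at the same rate as those still on drug. It estimates risk in a hypothetical setting where nobody leaves treatment for another reason.

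The distinction matters here because exit is expected to be fast. The Protocol synopsis says of relapsed disease: "A majority of patients will have progression of their disease within 2 to 3 months of starting treatment for relapsed disease". Dose modification is part of a named secondary safety endpoint. A Kaplan-Meier median could be printed for an event that fewer than half of patients ever have, and would be read as a statement about tolerability.

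**Working it through.** The documents give no figure for these outputs, so there is nothing of the plan's own to reproduce. The check sizes the gap under stated assumptions.

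**Inputs**

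- Median time to stopping for other reasons, m: 2 to 3 months. This borrows the Protocol's historical time to progression as a stand-in for time to stopping rucaparib.
- Share of patients ever having a dose-modifying TEAE, P: 10% to 70%. This is an assumption; the documents give no rate.
- Constant hazards: h2 = ln 2 / m for stopping, and h1 = h2·P/(1 − P) for the TEAE. Write L = h1 + h2.

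**Formulas**

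- True cumulative incidence: CIF(t) = (h1/L)·(1 − exp(−L·t)).
- Kaplan-Meier complement, censored at treatment stop: 1 − exp(−h1·t).
- Kaplan-Meier complement, censored at last dose + 28 days (c = 28/30.44 = 0.92 month): 1 − [1 − CIF(c)]·exp(−h*·(t − c)) for t > c, with h* = h1/[1 + (h2/L)·(exp(L·c) − 1)]. Stopped patients stay in the risk set for a further 28 days, which dilutes the hazard.

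**Worked case: m = 2.5 months, h1 = 0.2 per month**

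- h2 = 0.693/2.5 = 0.277 and L = 0.477. Ever affected: 0.2/0.477 = 42%.
- At 3 months the true value is 0.419·(1 − exp(−1.432)) = 31.9%. Kaplan-Meier gives 1 − exp(−0.6) = 45.1%.
- At 6 months the true value is 39.5%. Kaplan-Meier gives 1 − exp(−1.2) = 69.9%.
- The Kaplan-Meier median is 0.693/0.2 = 3.5 months, although only 42% ever have the event.
- With the 28-day extension, CIF(c) = 14.9% and h* = 0.2/1.320 = 0.1515. Kaplan-Meier then gives 37.9% at 3 months and 60.6% at 6 months.

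**Other cases** (true / censored at stop / censored at stop + 28 days)

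| m (months) | P | 3 months | 6 months |
|---|---|---|---|
| 3 | 30% | 18.9 / 25.7 / 21.9% | 25.9 / 44.8 / 38.4% |
| 3 | 50% | 37.5 / 50.0 / 43.5% | 46.9 / 75.0 / 67.3% |
| 2 | 50% | 43.8 / 64.6 / 53.6% | 49.2 / 87.5 / 77.4% |

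**Range of the excess for m = 2 and 3, P = 10% to 70%**

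- Censored at stop: 2 to 23 points at 3 months, 6 to 38 points at 6 months.
- Censored at stop + 28 days: 1 to 14 points at 3 months, 4 to 29 points at 6 months.

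**Where the gap shrinks**

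- Slower stopping (m = 6): 0.6 to 7.5 points at 3 months.
- Early toxicity, with dose-modifying TEAEs confined to the first 2 months and a median stop of 4, 8 or 12 months over that period. For a Kaplan-Meier value of 40% and m = 8: h1 = −ln(0.6)/2 = 0.255, h2 = 0.087, CIF(2) = 37.0%, an excess of 3 points. Over Kaplan-Meier values of 20% to 60% the excess is 1 to 8 points.

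**Simulation** (200 patients, 1,000 runs, m = 3, P = 50%, censored at stop): at 3 months Kaplan-Meier gave 50.1% and Aalen-Johansen 37.5%; at 6 months 74.8% and 46.8%. The crude percentage was 49.9%, which matches the value set.

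**The case against.** A reader might infer that the trial's reported incidence of dose-modifying toxicity will be far too high. The documents do not support that, for three reasons.

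- Incidence is reported as crude counts and percentages in separate tables that Kaplan-Meier does not touch, and the simulation shows these to be unbiased.
- The bias needs patients to be censored when treatment stops, and the SAP does not write that rule. If all event-free patients were instead censored at data cut-off, they would stay in the risk set and the upward bias would not arise.
- The TEAE rate is assumed. The 2 to 3 months is a historical progression time on other treatments, Protocol section 5.4.3 allows rucaparib beyond progression, and scheduled scans start only at week 8. At the low end (P = 10%, m = 3) the 3-month gap is 5.4% against 7.4%, about 1.3 standard errors at n = 200 (SE = √(0.054·0.946/200) = 1.6 points).

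Section 11.1 also does not name Kaplan-Meier itself, and section 3 adds a safeguard: "The number of patients with events and the number of censored patients over time will also be displayed". An attentive reader could see that fewer than half of patients had the event.

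A second tempting reading is that the clock ends at the wrong point. It does not: the output's name and its definition both end at the start of the TEAE.

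Most of this limits the size and wording of the point. It does not remove it. Section 3 has no exception, and section 11.1 lacks the clause that lets DOR, PFS and OS fall back on descriptive statistics. With the TEAE window tied to the last dose, censoring at or soon after treatment stop is the natural reading. The crude tables are also not a full substitute, since none of the overall tables listed covers the composite including discontinuation.

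**Conclusion.** The point holds for the two time-to-first-TEAE outputs and no further. They fall under Kaplan-Meier by default, and the censoring rule that section 10.1 refers to is missing. That gap depends on no assumption. If patients are censored at treatment stop, the curve overstates cumulative risk and the median comes too early.

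The direction is certain under that rule, but the size is not. It is about 2 to 23 points at 3 months and 6 to 38 at 6 months for a median stop of 2 to 3 months with constant hazards and 10% to 70% ever affected. It is smaller if censoring waits until 28 days after the last dose, and 1 to 8 points if toxicity is early and few patients stop before the first scan.

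This is a descriptive secondary safety summary. The crude TEAE tables, the ORR analysis and the interim rules are untouched.

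**What to change.** In SAP section 11.1, for both variables:

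- Summarise by the cumulative incidence function (Aalen-Johansen) in place of Kaplan-Meier.
- Treat as competing events permanent discontinuation of rucaparib for any reason other than the event of interest, and death.
- Censor only patients still on rucaparib without the event at data cut-off.
- Report cumulative incidence at fixed times, for example 1, 3 and 6 months, with 95% CI, and drop the Kaplan-Meier median.
- Add a crude number and percentage for the composite including discontinuation.
- Keep the clock ending at the start of the TEAE, as now defined.

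No new data are needed: Protocol section 3.1.3 already requires the date and reason for stopping rucaparib in the eCRF. The cost is SAP wording and a little more programming. The curves will also not be on the Kaplan-Meier scale used for the other time-to-event outputs, which a footnote should say.
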